Protocol Overview/Synopsis	
Eligible participants in the original RCT who agree to be part of the Extension Study will sign the informed consent form.
 
• Participants assigned to the original RCT SAP group will initiate use of the CLC system for 3 months.• Participants assigned to the original RCT CLC group will be randomly assigned 1:1 to either continue CLC or switch to PLGS for 3 months.• After 3 months, all participants will be given the opportunity to use the CLC system until the point that the system becomes commercially available

[figure not shown]
[figure not shown]

Figure 1: Study Design - Participants entering Extension Study after having completed preceding 6-month RCT. Participants in the original RCT SAP Group will use CLC in the first 3 months of the Extension Study while participants in the original RCT CLC Group will be randomly assigned 1:1 to either continue CLC or switch to PLGS. After 3 months, all participants will be given the opportunity to use CLC until the point that the CLC system becomes commercially available.

193

SCHEMATICS OF STUDY DESIGN

194

Figure 2: Schematic of Eligibility Assessment/Enrollment

195

196

[figure not shown]
197
198
Figure 3. Schematic of Study Design

Table 1. Schedule of Study Visits and Procedures

	0 Weeks	1w	2w	13w	26w, then every 13 weeks until end	Final Visit
Visit (V) or Phone (P)	V	P¹	P¹	V	V	V
Comment	Screen/Enroll and Rand/Assign					
Eligibility Assessment	X					
HbA1c (DCA Vantage or similar point of care device, or local lab)	X²			X	X	X
HbA1c (Central lab)	X²			X		
Pregnancy test (females of child-bearing potential)	X			X	X	
Device Data download(s)		X	X	X	X	X
Review diabetes management and AEs		X	X	X	X	X
Questionnaires as defined in section 5.2	X²			X	X³	X
Follow-up Phone Call						P

200 ¹ Only performed for those participants who switched from SAP in the original 6-month RCT to CLC in the Extension Study, or from CLC in the
 201 original RCT to PLGS in the Extension Study

202 ² Will use results obtained at Final Visit of preceding 6-month RCT

203 ³ 26-Week visit only

204

Chapter 1: Background Information

205

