655 **3.8.1 1- and 2-Week Phone Contacts**

656 For those participants who switched from SAP in the original RCT to CLC in the Extension
657 Study, or from CLC in the original RCT to PLGS in the Extension Study, study staff will
658 perform a phone call with the participant within 7 (± 3) days and at 14 (± 3) days following group
659 assignment.

660 If the participant cannot be reached, the participant's other contact methods will be utilized,
661 including the emergency contact.

662 The following will occur during each contact:

- 663 • Review of available CGM and/or system data to identify any safety issues associated
664 with insulin pump settings and current diabetes management approach
665 • Assessment of adverse events, adverse device effects, and device issues
666 • Optimization of pump settings, if indicated

667 At investigator discretion, either phone contact may be replaced by a clinic visit. Additional
668 phone contacts or clinic visits may be performed as needed.

669 **3.8.2 Data Uploads**

670 Participants will be instructed to upload data from their study insulin pump prior to the 1- and 2-
671 week phone contacts (if applicable) and at least every 4 weeks for the remainder of the study.
672 Participants will be provided with any software and hardware needed to perform these data
673 uploads.

674 If participating in the menstrual cycle data collection aspect of the study, participants may
675 periodically be asked to transmit the collected data to the clinical site using the export
676 functionality of the phone app that was used.

677 **3.8.3 13-Week Visit**

678 All participants will return to the clinic for a 13-Week (± 7 days) clinic visit during which the
679 following will occur:

- 680 • HbA1c determination using the DCA Vantage or similar point of care device
681 • Collection of a blood sample to send to the central laboratory for HbA1c determination
682 • Completion of questionnaires
683 • Urine pregnancy test for all women of child-bearing potential
684 • Weight measurement
685 • Assessment of adverse events, adverse device effects, and device issues
686 • Download of device data (study system or personal pump and study CGM, study BG meter,
687 study ketone meter)

688

689 All participants will be offered the opportunity to continue in the study, using the CLC system
690 until such time that the system becomes commercially available.

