975 6. Diabetic ketoacidosis (DKA) as defined below or in the absence of DKA, a hyperglycemia or
976 ketosis event meeting the criteria defined below

977 Hypoglycemia and hyperglycemia not meeting the criteria below will not be recorded as adverse
978 events unless associated with an Adverse Device Effect. Skin reactions from sensor placement
979 are only reportable if severe and/or required treatment.

980 Pregnancy occurring during the study will be reported as an AE (see section 6.3).

981 All reportable AEs—whether volunteered by the participant, discovered by study personnel
982 during questioning, or detected through physical examination, laboratory test, or other means—
983 will be reported on an AE form online. Each AE form is reviewed by the Medical Monitor to
984 assess safety and to verify the coding and the reporting that is required.

985 **6.1.2.1 Hypoglycemic Events**

986 Hypoglycemia not associated with an Adverse Device Effect is only reportable as an adverse
987 event when the following definition for severe hypoglycemia is met: the event required
988 assistance of another person due to altered consciousness, and required another person to actively
989 administer carbohydrate, glucagon, or other resuscitative actions. This means that the participant
990 was impaired cognitively to the point that he/she was unable to treat himself/herself, was unable
991 to verbalize his/ her needs, was incoherent, disoriented, and/or combative, or experienced seizure
992 or loss of consciousness. These episodes may be associated with sufficient neuroglycopenia to
993 induce seizure or loss of consciousness. If plasma glucose measurements are not available
994 during such an event, neurological recovery attributable to the restoration of plasma glucose to
995 normal is considered sufficient evidence that the event was induced by a low plasma glucose
996 concentration.

997 **6.1.2.2 Hyperglycemic/Ketotic Events**

998 Hyperglycemia not associated with an Adverse Device Effect is only reportable as an adverse
999 event when one of the following 4 criteria is met:

- 1000 • the event involved DKA, as defined by the Diabetes Control and Complications Trial
1001 (DCCT) and described below

- 1002 • evaluation or treatment was obtained at a health care provider facility for an acute event
1003 involving hyperglycemia or ketosis
- 1004 • blood ketone level ≥ 1.0 mmol/L and communication occurred with a health care provider
1005 at the time of the event

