18 **Table 2: Schedule of Visits and Procedures**

19

	0 Weeks	1w	2w	13w	26w, then every 13 weeks until end	Final Visit
Visit (V) or Phone (P)	V	P ¹	P ¹	V	V	V
Comment	Screen/Enroll and Rand/Assign					
Eligibility Assessment	X					
HbA1c (DCA Vantage or similar point of care device, or local lab)	X ²			X	X	X
HbA1c (Central lab)	X ²			X		
Pregnancy test (females of child-bearing potential)	X			X	X	
Device Data download(s)		X	X	X	X	X
Review diabetes management and AEs		X	X	X	X	X
Questionnaires	X ²			X	X ³	X
Follow-up Phone Call						P

20
21 ¹ Only performed for those participants who switched from SAP in the original 6-month RCT to CLC in the
22 Extension Study, or from CLC in the original RCT to PLGS in the Extension Study
23 ² Will use results obtained at Final Visit of preceding 6-month RCT

24 ³ 26-Week visit only

25

26

27

2. Objective 1

28 Among individuals who used CLC in the preceding 6-month RCT, to compare continued use of CLC
29 (t:slim X2 with Control-IQ Technology) for 3 months versus switching to a Predictive Low-Glucose
30 Suspend (PLGS) system (t:slim X2 with Basal-IQ Technology) for 3 months.31

- 32 Design and Primary Outcome: RCT with 1:1 randomization to intervention with CLC vs.
33 PLGS for 3 months. All analyses (treatment group comparisons) will be considered
34 exploratory/hypothesis-generating. Consequently, there will not be an attempt to adjust for
35 multiplicity. Time-in-range 70-180 mg/dL will be considered the primary exploratory
outcome.
- 36 Sample Size: The sample size will depend on how many subjects complete
37 the preceding 6-month RCT and consent to participate in the extension.
38 However, it is expected that about 100 subjects will be enrolled and
39 randomized for Objective 1.

40

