235 Local HbA1c values measured at the site will be included as an auxiliary variable (analogous to
236 imputing any missing lab values). Regression diagnostics will be employed as described earlier.

237 For the binary HbA1c outcomes listed above, risk-adjusted percentages by treatment group will be
238 computed from a logistic regression model. The logistic regression will adjust for the same factors
239 mentioned above for the analysis with HbA1c as a continuous factor.

240

241

242 **2.6. Questionnaires, Insulin, Weight, and BMI Analyses**

243

244 For questionnaires, insulin, weight, and BMI metrics comparisons between treatment arms will be made
245 using similar methods as described above for the primary analysis.

246

247

248 **2.7. Safety Analyses**

249 All enrolled and randomized participants will be included in these analyses and all their safety events up
250 to the 13-week visit will be reported.

251 The circumstances of all reportable cases of the following will be summarized and tabulated by
252 treatment group:

- 253 • Severe hypoglycemia
- 254 • Diabetic ketoacidosis
- 255 • Ketone events defined as a calendar day with ketone level >1.0 mmol/L
- 256 • CGM-measured hypoglycemic events (defined as at least 15 consecutive minutes <54
257 mg/dL)
- 258 • CGM-measured hyperglycemic events (defined as at least 120 consecutive minutes >300
259 mg/dL)
- 260 • Worsening of HbA1c from randomization to 13 weeks by $>0.5\%$
- 261 • Serious adverse events with a possible or greater relationship to a study device (including
262 anticipated and unanticipated adverse device effects)
- 263 • Other serious adverse events not related to a study device
- 264 • Adverse device effects (ADE) that do not meet criteria for SAE

265
266 For the following outcomes, mean \pm SD or summary statistics appropriate to the distribution will be
267 tabulated by treatment group:

- 268 • Number of SH events and SH event rate per 100 person-years
- 269 • Number of DKA events and DKA event rate per 100 person-years
- 270 • Any adverse event rate per 100 person-years

271 If there are at least 10 events across both treatment arms, the numbers will be compared between the two
272 treatment arms using a robust Poisson regression and the percentage of subjects with at least one event
273 will be compared using logistic regression. The regression will adjust for site as random effect. The
274 amount of follow up will be included as an offset covariate to compare the rates.

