
275 The analyses for the two continuous CGM-measured outcomes will parallel those mentioned above for
276 the primary outcome and the worsening in HbA1c will parallel the binary HbA1c models mentioned
277 above.

278 279 **2.8. Device Issues**

280 Reported device issues for each type of study device (e.g., closed-loop system, PLGS system, CGM) by
281 treatment group.

282 283 284 **2.9. Protocol Adherence and Retention**

286 The following tabulations and analyses will be performed by treatment group to assess protocol
287 adherence for the study:

- 288 • Listing of all protocol deviations
- 289 • Tabulation of protocol-specified visits and phone contacts completed in window, out of window and missed for each visit/phone contact
- 290 • Flow chart accounting for all enrolled and randomized participants up to week 13
- 291 • Flow chart of all randomized participants at all scheduled visits and phone contacts to assess visit, and phone completion, and study completion rates
- 292 • Number of and reasons for unscheduled visits and phone calls
- 293 • Number of participants who stopped treatment (CLC or PLGS) and reasons
- 294
- 295
- 296
- 297

298 **2.10. Baseline Descriptive Statistics**

299
300 Baseline demographic and clinical characteristics of the cohort of all randomized participants will be
301 summarized in a table using summary statistics appropriate to the distribution of each variable.
302 Descriptive statistics will be displayed overall and by treatment group.

303
304 Will include:

- 305 • Age at randomization
- 306 • Gender
- 307 • Race/ethnicity
- 308 • Diabetes duration at randomization
- 309 • HbA1c at the end of preceding 6-month RCT
- 310 • BMI at the end of preceding 6-month RCT
- 311
- 312

313 **2.11. Other Tabulations**

314
315 Individual listings for each randomized participant will include the following:

- 316 • Treatment group, age, gender, race/ethnicity, duration, height, weight, and BMI at randomization
- 317
- 318 • Pre-existing medical conditions other than diabetes
- 319 • Medication at enrollment/randomization
- 320 • Baseline glucose metrics
- 321

322 The following tabulations and analyses will be performed by treatment group:

323 • Sensor performance metrics (difference, absolute relative difference, and International
324 Organization for Standardization criteria)

325 • % time CGM data available to the system

326

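### Within the randomized comparison only the PLGS arm is asked about events at weeks 1 and 2, so the any-adverse-event comparison and the by-arm device tables mix device effect with unequal questioning

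*SAP*

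**What the plan says.** **Who is contacted.** Footnote 1 to Protocol Table 1 reads "Only performed for those participants who switched from SAP in the original 6-month RCT to CLC in the Extension Study, or from CLC in" and goes on to name those who moved from CLC to PLGS. Footnote 1 to SAP Table 2 sets the same limit. Protocol 3.8.1 repeats it in the text: "Study, or from CLC in the original RCT to PLGS in the Extension Study, study staff will" make the calls at 7 (±3) and 14 (±3) days after assignment. The continuing-CLC arm is not included.

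**What each contact covers.** Protocol 3.8.1 lists "Assessment of adverse events, adverse device effects, and device issues". It also lists a review of CGM or system data for safety issues, and "Optimization of pump settings, if indicated".

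**When both arms are next assessed.** The next scheduled assessment of adverse events and device issues for either arm is the 13-week visit (Protocol 3.8.3).

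**What is compared.** SAP 2.7 lists three outcomes directly above its testing rule: severe hypoglycemia, DKA and any adverse event, each as a rate per 100 person-years. The rule is: "If there are at least 10 events across both treatment arms, the numbers will be compared between the two" treatment arms by robust Poisson regression, and the percentage with at least one event by logistic regression. The models include site as a random effect, with amount of follow-up as an offset for the rates. Protocol 8.5 says the same. Non-serious adverse device effects are tabulated by arm in SAP 2.7. SAP 2.8 covers device issues: "Reported device issues for each type of study device (e.g., closed-loop system, PLGS system, CGM) by" treatment group.

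**What is not said.** The sensitivity analyses in SAP 2.3.2 deal with baseline imbalance and missing data. Neither document mentions that scheduled questioning differs between the randomized arms.

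**The concern.** Protocol 6.1.2 counts an adverse event whether it is volunteered, found on questioning or detected in another way, so capture depends partly on how often participants are asked. Randomization does not protect against this, because the difference in questioning starts after assignment and follows the arm. The follow-up offset corrects for length of observation, not for how closely participants are observed.

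If some early events would be forgotten or never raised by week 13, they are recorded more completely on PLGS. Taken alone, that inflates PLGS counts relative to the investigational device even when true rates are equal. Obtaining additional safety data is a stated aim (Protocol 1.2), so a reader of the by-arm tables should know that the counts were not gathered on equal terms.

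**Working it through.** The plan gives no event rate, power or capture figure for this comparison, so there is no stated number to reproduce.

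**1. Scheduled assessments after randomization, through week 13**
- PLGS: weeks 1, 2 and 13, so 3.
- Continuing CLC: week 13, so 1.

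**2. Which outcomes are exposed**
- CGM-measured events and HbA1c worsening come from device or laboratory data and have their own models at the end of SAP 2.7. They do not depend on being asked.
- Severe hypoglycemia and DKA are salient events that are likely to be reported whenever asked about.
- That leaves the any-adverse-event rate among the outcomes listed above the 10-event rule, plus two sets of tables: non-serious adverse device effects and device issues.

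**3. When the test would run**
- Inputs: about 100 randomized 1:1 (Protocol 8.2), so 50 per arm; 91 days.
- Person-time = 2 × 50 × 91 / 365.25 = 24.9 person-years.
- Ten events correspond to 10 / 24.9 = about 40 per 100 person-years.
- Poisson probability of at least 10 events: below 0.001 at 10 per 100 person-years, 0.03 at 20, 0.54 at 40 and 0.99 at 80.
- The test is therefore most likely to run for the most frequent category, any adverse event, which is also the one most dependent on questioning.

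**4. Size of the ascertainment effect alone (assumptions, not document figures)**
- Assume equal true rates in both arms, a share s of events in the first 14 days, full capture of those events on PLGS, and capture c for every other event in either arm.
- Spurious PLGS:CLC rate ratio = [s + (1 − s)c] / c.
- Events spread evenly: s = 14/91 = 0.154.
  - c = 0.9: (0.154 + 0.846 × 0.9) / 0.9 = 1.02
  - c = 0.7: (0.154 + 0.846 × 0.7) / 0.7 = 1.07
  - c = 0.5: (0.154 + 0.846 × 0.5) / 0.5 = 1.15

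**5. Effect on the test**
- Simulated Poisson counts, two-sided 0.05 (the SAP gives no alpha; 0.05 is assumed from its 95% intervals), given at least 10 events.
- With 30 expected events, the false-positive rate is 4.4% at a ratio of 1.0, 5.4% at 1.1 and 9.8% at 1.3.
- With 60 expected events, it is 4.8%, 6.0% and 16.5%.

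**6. When scheduled questioning becomes equal**
- The second call window closes on day 14 + 3 = 17. From day 18 both arms have only the week-13 assessment.
- Days 0 to 17 inclusive are 18 days, and 18/91 = 19.8% of person-time.

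**The case against.** **Both arms have other routes for reporting.** All participants are asked to call staff about health or technical problems (Protocol 3.8). All upload pump data at least every 4 weeks (3.8.2), and unscheduled visits are open to all (3.10). This stands. It argues for high capture in both arms and so for the lower end of the range, but it does not equalize scheduled questioning.

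**Reportable events are mostly notable.** Protocol 6.1.2 and 6.2 leave out skin reactions that need no treatment and routine device problems. This also stands, and points the same way.

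**The comparisons are exploratory, and contacts are visible.** SAP 2.2 labels all arm comparisons hypothesis-generating, and SAP 2.9 tabulates visits and calls by arm. This lowers the stakes. The label explains the lack of multiplicity adjustment; it does not tell a reader that counts were collected unequally.

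Three stronger readings are tempting and are not supported:
- *A reader might infer that the safety comparison is biased in favor of CLC.* Ascertainment alone would push that way. But the same calls include a safety review and pump-setting optimization on PLGS only, which could prevent PLGS events. The net direction is not established.
- *A reader might infer that the ketone criterion is itself driven by the calls, since it needs "mmol/L and communication occurred with a health care provider".* The communication must occur at the time of the event (Protocol 6.1.2.2), so a scheduled call would have to coincide with it. Protocol 4.2.4 already tells participants who find ketones above 0.6 mmol/L on its checking pathway to contact staff, without regard to arm.
- *A reader might infer a large distortion.* A ratio of 1.36 needs only 30% capture without the calls. A ratio of 1.50 needs 50% capture and half of all events in the first two weeks in both arms. Nothing in the documents supports either.

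**Conclusion.** The concern holds within limits and is minor. It is certain from both documents that scheduled assessment is three times on PLGS and once on continuing CLC, and that SAP 2.7 and 2.8 make no allowance for this. It affects the any-adverse-event comparison and the by-arm tables of non-serious adverse device effects and device issues. The device-issue table is descriptive, so no test is at risk there.

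The size is a matter of assumption: a spurious ratio of about 1.02 to 1.15 for capture of 90% down to 50%, given equal true rates, an even spread of events and full early capture on PLGS. At a ratio near 1.1 the test's error rate barely moves. The result does not undermine the other Objective 1 safety outcomes, and the documents do not show which arm the combined effect of the calls favors.

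**What to change.** Keep the all-days analyses in SAP 2.7 and 2.8 as planned, and add two things:

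- A sensitivity version of the any-adverse-event comparison, and of the adverse device effect and device-issue tables, limited to events with onset, and person-time, from day 18 onward in both arms.
- A sentence beside the all-days results stating that scheduled ascertainment and contact, including pump-setting optimization, were unequal by arm.

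Apply the same 10-event rule to the sensitivity version, and show counts and rates without a test if fewer remain. Person-time falls to 100 × 73 / 365.25 = 20.0 person-years, so 10 events then correspond to about 50 per 100 person-years.

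The cost is a few lines of SAP text and one repeated set of tables. It needs onset dates for adverse events and device issues, which I assume are recorded. No change to conduct is involved; the SAP's version history places the study past the initial 3 months. The downside is the loss of about 20% of person-time, including the early period after the switch, when a real effect of changing device is most plausible. The sensitivity version therefore supplements the all-days result and does not replace it.
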